**g) Follow Up Phone Call – within 6 weeks**

Women will be contacted by telephone to check in to see how mom and baby are doing and to document any new outcomes on the study outcomes form including hospitalizations and deaths.

**h) Follow Up Phone Call or Visit for Infant Outcomes – Every 3 months until 1 year**

Women will be contacted by phone every three months to ask how the baby is growing. Information from medical visits about the baby's height and weight will be asked as well as any information about infant hospitalizations or sick clinic visits or death. Women will be encouraged to bring the baby to the clinic for a visit at 6 months and 12 months to measure height, weight and head circumference.

## Study Forms

Form #	Form Name
0	Forms List
1	Screening Log
2	Eligibility Assessment
3	Consent
4	Randomization Data Form
5	Enrollment Visit Baseline Survey
6	Follow Up Visit Questionnaire
7	Medication Adherence Questionnaire
8	Sick Call Visit Questionnaire
9	Study Outcomes Including Labs
10	Adverse Event Form
11	Postpartum Check In Form
12	Participant Follow Up and Call Log
13	Infant Follow Up Form

## VIII. TRAINING AND QUALITY ASSURANCE

Study staff (RN, data manager, study coordinator) must have the human subject's protection training certificate. New staff members will undergo training on research ethics. Additional training will occur on site prior to study initiation related to study procedures, forms, data entry, sample collection and subject follow up. Specific training will be provided to midwives about how to assess for congenital anomalies at birth.

The participating site is responsible for conducting routine quality assurance (QA) and quality control (QC) activities to internally monitor study progress and protocol compliance. The site PI will provide direct access to all trial-related sites, source data/data collection forms, and reports. The site PI will ensure all study personnel are appropriately trained and applicable documentations are maintained on site.

Data QC checks will be run on the database. Any missing data or data anomalies will be communicated to the site(s) for clarification and resolution.

## IX. MONITORING OF ADVERSE EVENTS

### a) Reporting

#### **Adverse Event:**

An adverse event is any untoward medical occurrence in a subject administered a pharmaceutical product regardless of its causal relationship to the study treatment. The occurrence of an AE may come to the attention of study personnel during study visits and interviews of a study recipient presenting for medical care.

All AEs not meeting the criteria for SAEs should be captured on the appropriate form. Information to be collected includes event description, clinician's assessment of severity, relationship to study product, and time of resolution/stabilization of the event. All AEs occurring while on study must be documented appropriately regardless of relationship. All AEs will be followed to adequate resolution.

Any medical condition that is present at the time that the subject is screened should be considered as baseline and not reported as an AE. However, if it deteriorates at any time during the study, it should be recorded as an AE.

All AEs must be graded for severity and relationship to study product.

**Severity of Event:** All AEs will be assessed by the clinician using a grading system.

**Mild:** events require minimal or no treatment; do not interfere with the subject's daily activities.

**Moderate:** events result in a low level of inconvenience or concern with the therapeutic measures; may cause some interference with functioning.

**Severe:** events interrupt a subject's usual daily activity and may require systemic drug therapy or other treatment; are usually incapacitating.

**Relationship to Study Products:** The clinician's assessment of an AE's relationship to the study drug is part of the documentation process.

- **Related** – There is a reasonable possibility that the study drug caused the AE.  
Reasonable possibility means that there is evidence to suggest a causal relationship between the study drug and the AE.
- **Not Related** – There is not a reasonable possibility that administration of the study drug caused the AE.

#### **Serious Adverse Event (SAE):**

An AE or suspected adverse reaction is considered "serious" if, in the view of either the investigator, it results in any of the following outcomes:

- Maternal death
- Neonatal death

- Stillbirth
- Congenital anomalies
- Unanticipated or prolonged maternal hospitalization (longer than expected)
- Prolonged neonatal hospitalization (longer than expected based on gestational age at birth)

All SAEs will be:

- Assessed for severity and relationship to study product and alternate etiology by a study physician.
- Recorded on the appropriate form
- Followed through resolution by a licensed study physician.
- Reviewed and evaluated by the DSMB and the IRB.

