**b) Data Safety Monitoring Board (DSMB)**

Safety oversight will be conducted by a DSMB that is an independent group of experts that monitors subject safety. The DSMB members will be separate and independent of study personnel participating in this trial and should not have scientific, financial, or other conflict of interest related to the study. The DSMB will consist of three members with appropriate expertise to contribute to the interpretation of the data from this trial: malaria in pregnancy, maternal-fetal medicine and biostatistics.

The DSMB will review and approve the study protocol and safety plan prior to initiation of the trial. It will be convened when 50% of the planned subjects have been enrolled for a review of interim data. The PI will review safety data weekly and report any serious adverse events to the DSMB and IRB and to NIH/NICHD. The DSMB and NIH will receive quarterly adverse event reports and the interim report will include the following information: recruitment, withdrawals, loss to follow up, adverse events, and medication tolerance. The DSMB will also review efficacy and safety data after all subjects have been enrolled in a final closeout meeting, held at the end of the study. As an outcome of each review/meeting, the DSMB will make a recommendation as to the advisability of proceeding with study and to continue, modify, or terminate the study.

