### XIV. ETHICAL CONSIDERATIONS

- a) The protocol will be reviewed by the Institutional Review Board in Cameroon at CBCHS (Cameroon Baptist Convention Health Services). This is an active and long-standing IRB group that meets regularly and reviews all research protocols for work proposed to

take place at CBCHS facilities. The protocol will also be reviewed by the IRB at the University of Alabama at Birmingham but the primary IRB will be located in Cameroon. Any changes or edits to the protocol will be submitted to both IRB groups and both will be informed of any serious adverse events that occur during the study.

- b) Informed Consent Process: Women will be invited to participate and provide informed consent. Anyone 16 years of age or older will be eligible to participate according to Cameroon law which grants “mature minor” status to girls during pregnancy and this allows them to consent without parental involvement.

Malaria detected as part of the study (whether a screening test or a test done in the setting of a fever work up) will be treated with quinine per clinical routine. Positive tests for STIs (GC/CT and syphilis) identified at the end of pregnancy will be treated per CDC recommendations. GBS colonization will be treated with ampicillin IV during labor and delivery for women with facility deliveries. The cost of treatment for infections detected or adverse events as a result of testing or treatment performed for the study will be covered as a part of study expenses but hospitalization and other diagnostic and treatment costs will not be covered.

Women will have the option in the consent of whether or not to submit samples to long term storage and later testing on dried blood spots, vaginal swabs and placental biopsies and infant follow up procedures. No blood or samples will be collected from infants.

- c) Participant confidentiality. Given the personal and serious nature of working with a population of pregnant subjects with HIV infection, study related conversations will occur in private although participants will be invited to include a support person in the discussion if they prefer. Subjects will have code numbers and will not be identified by name. The staff at CBCHS is very well versed in caring for women with HIV-infection and they prioritize confidentiality at the highest level in all clinical and research activities and documentation. Subjects will have code numbers and will not be identified by name.

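### The SAE list has no criterion for a life-threatening or disabling maternal event managed without admission, so no individual DSMB or IRB review of such an event is required

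*Combined protocol and SAP*

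**What the plan says.** Section IX.a (Serious Adverse Event) makes an event serious if, "in the view of either the investigator, it results in any of the following outcomes". Six outcomes follow. For the mother they are "Maternal death" and "Unanticipated or prolonged maternal hospitalization (longer than expected". The other four concern the fetus or newborn: neonatal death, stillbirth, congenital anomalies and prolonged neonatal hospitalization. Every SAE is to be assessed by a study physician, including for another cause, and then "Reviewed and evaluated by the DSMB and the IRB".

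Section IX.a (Adverse Event) sends all other events to a form, with a clinician's grading of severity and relatedness, and follows them to resolution. The top grade, Severe, covers events that "may require systemic drug therapy or other treatment; are usually incapacitating". There is no separate life-threatening grade, and neither severity nor relatedness changes how an event is reported.

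Section IX.b sets the reporting routes. For SAEs: "The PI will review safety data weekly and report any serious adverse events to the DSMB and IRB and to NIH/NICHD". For adverse events generally: "The DSMB and NIH will receive quarterly adverse event reports". The interim report at 50% enrollment also carries adverse events and medication tolerance. Section XII (Data Management) adds that the PI's weekly review is blinded to arm. Section XIV.a tells both IRBs about SAEs and protocol changes, and names nothing else.

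On costs, section XIV.b says that the study pays for treating adverse events caused by its testing or treatment, "but hospitalization and other diagnostic and treatment costs will not be covered".

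**The concern.** Seriousness normally reflects how grave an event is. Here, for a non-fatal event in the mother's own health, it turns on one administrative fact: whether she was admitted, or kept in longer than expected. Two women with the same life-threatening allergic reaction would be classified differently if one was admitted and the other was treated and sent home.

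This matters because maternal tolerance, with rash and allergic reactions named, is a primary outcome of Aim 3 (section III.a), and the Background says that more data on the combination are needed. The protocol also foresees severe reactions: section V.c excludes women with a past severe adverse reaction to either drug. After five minutes of observation at the clinic, women take the day 2 and day 3 doses at home (section VI.b), so a later reaction may first be seen at a sick call. At stake are the completeness of the maternal SAE record and the assurance that independent bodies look individually at the gravest maternal reactions.

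**Working it through.** No sample size, rate or power figure is involved, so the check is a count and a side-by-side reading.

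**1. Count the criteria in section IX.a.**
- Mother's own condition: death, hospitalization = 2.
- Fetus or newborn: neonatal death, stillbirth, congenital anomalies, prolonged neonatal hospitalization = 4.
- Total: 2 + 4 = 6.
- Non-fatal criteria on the mother's own condition: 2 − 1 = 1, namely hospitalization.
- Criteria covering a life-threatening or disabling maternal event without admission: 0 of 6.

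**2. Is the list closed?** The wording ties seriousness to any of the outcomes that follow. The investigator's view decides whether a listed outcome has occurred. Nothing lets the investigator add an outcome, and there is no general clause for medically important events.

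**3. Does another section fill the gap?** The severity scale, the DSMB section, the data management text and the ethics section add no criterion for seriousness. A Severe grade combined with a Related judgement still leaves an event non-serious if no listed outcome follows.

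**4. Follow one event through both routes.** Take a life-threatening maternal reaction with no death, no admission and no listed fetal or neonatal outcome.

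| Step | If it were an SAE | As the text stands |
|---|---|---|
| Grading of severity and relatedness | Yes, by a study physician | Yes, by the clinician |
| Assessment of another cause | Required | Not stated |
| PI's weekly blinded review | Yes | Yes |
| Individual DSMB review | Required | Not required |
| Report to NIH | Individual report by the PI | Quarterly report |
| Report to the two IRBs | Required | No route stated |
| DSMB quarterly and interim reports | Yes | Yes |

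The loss is in three places: physician assessment of another cause, individual DSMB review and notice to the IRBs. The event is not lost from the trial's records.

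**5. The cost sentence.** Its first part covers treatment of adverse events that result from study testing or treatment. Its second part excludes hospitalization and other treatment costs. An admission for a study drug reaction falls under both, so the sentence does not settle who bears that cost.

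**The case against.** The strongest reply is that the gap is narrow and already mitigated. Both sites are hospitals, and sick calls go to a maternity unit that is open at all hours (section VII.c). Any unanticipated admission counts, with no minimum stay, so most life-threatening reactions would probably become SAEs anyway. All adverse events are graded and followed, the PI sees them weekly, and the DSMB sees them quarterly and at the interim review. Section IX.b also mentions a safety plan approved by the DSMB; if that is a separate document, it may contain further criteria. All of this limits the size of the problem. It does not supply the missing criterion: the PI is blinded, belongs to the study team, and is required to pass on only SAEs individually.

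Four stronger readings are tempting and should not be adopted.
- *A non-fatal maternal event is serious only if she is admitted.* Too strong. A maternal event that leads to stillbirth, neonatal death, a congenital anomaly or a prolonged neonatal stay is also serious.
- *Women must pay for admission, so ability to pay decides what counts as serious.* Section XIV.b says what the study will not cover, not who pays, and the same sentence covers study-related adverse events. The consent pages, which may say more, were not available. The chain from cost to no admission to a missed SAE is inference, with no figure behind it.
- *The harm can be sized by the women enrolled while a quarterly report is awaited.* That counts one quarter's recruitment. It ignores the weekly review, and no deadline is stated for SAE reports to the DSMB, so the delay avoided cannot be calculated.
- *Every severe and related event should be an SAE.* This merges severity with seriousness. The Severe grade could take in vomiting, dizziness or weakness, which are expected tolerance outcomes.

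**Conclusion.** The point holds as a defect in a stated rule. Under the current definition, a life-threatening or persistently disabling maternal reaction managed without admission, and without a listed fetal or neonatal outcome, is non-serious. It gets no required individual DSMB review and has no stated route to either IRB. Of the six criteria, none covers it.

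The frequency of such events cannot be estimated from the documents and may well be low. The case for the change rests on how grave the events are and how little the change costs, not on a count. The conclusion assumes that the list is read as written and that no separate safety plan or consent text adds criteria. It does not depend on the cost sentence, which is a separate ambiguity. The change should be made, but the gap does not threaten the efficacy analysis.

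**What to change.** Add two criteria to the SAE list in section IX.a, for the mother and regardless of admission: any life-threatening event, and any event causing persistent or significant disability. Handle them through the existing SAE route to the study physician, the DSMB, both IRBs and NIH/NICHD. If a separate safety plan exists, align it with the same list.

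Separately, reconcile the two halves of the cost sentence in section XIV.b, so that it states whether hospital care for an adverse event resulting from study testing or treatment is covered, and check that the consent form says the same.

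The cost is a protocol amendment to both IRBs and some extra individual SAE reports. Their number should be small, because only events managed wholly without admission are added, but that is an expectation and not an estimate. The SAE change needs no new visit, test or reporting route. The cost wording needs only a decision on which half is meant.

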### c) Protocol Summary

We plan a test-of-concept of our central hypothesis by conducting a randomized, placebo-controlled, double-blinded, Phase II trial with the following 3 aims:

Aim 1: Test the efficacy of a combination malaria prophylaxis regimen (TMPS-AZ) compared to the standard of care regimen (TMPS) in reducing malaria in HIV-infected pregnant women. The goal is to determine whether the addition of azithromycin has an impact on the proportion with submicroscopic parasitemia at delivery.

Approach: Pregnant women with HIV will be randomized to the intervention (TMPS-AZ) or to usual care (TMPS) with monthly follow-up visits to receive medications. Blood collected at delivery will be tested by PCR to assess for infection with *Plasmodium falciparum*.

Aim 2: Measure the reduction in prevalence of curable bacterial STIs and GBS colonization after 35 weeks gestation (or at delivery) in the intervention and usual care groups. The goal is to measure the impact of monthly AZ prophylaxis on the prevalence of pathogens that are associated with adverse birth outcomes (*Neisseria gonorrhoeae*, *Chlamydia trachomatis*, *Treponema pallidum*, *Streptococcus agalactiae*).

Approach: Participants will have vaginal and anogenital swabs in late pregnancy or at delivery for GC/CT/GBS nucleic acid amplification testing. Blood will be collected simultaneously for syphilis testing.

Aim 3: Determine the fetal/neonatal safety and adherence/tolerability of TMPS-AZ compared to TMPS. The goal is to collect safety, adherence and tolerability data for this novel regimen used in HIV-infected pregnant women.

Approach: Birth outcomes will be captured by chart review and women will fill out a validated questionnaire to assess medication adherence and tolerance at each visit. The first dose of medication at each visit will be given under directly observed therapy.

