#### a) Primary Outcomes

**Aim 1** Proportion of women with *Plasmodium falciparum* peripheral parasitemia by microscopy or PCR.

**Aim 2** Prevalence of a composite STI measure (GC, CT, syphilis infections) will be measured in both groups in late pregnancy (>35 weeks gestation) or at delivery and compared between the two groups.

[figure not shown]
**Aim 3** a) Mean infant birthweight; b) Proportion with adverse birth outcomes, including low infant birthweight (<2500 gm), miscarriage (<28 weeks), preterm delivery (<37 weeks), small for gestational age (SGA), stillbirth (>28 weeks), congenital anomaly at birth, early neonatal mortality (within 7 days); and c) maternal adherence to and tolerance of the prophylactic regimen (vomiting, rash/allergic reactions, dizziness, weakness).

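### The SAE list omits miscarriage and infant death after the neonatal period, so neither event by itself triggers event-level reporting or notice to the IRBs

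*Combined protocol and SAP*

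**What the plan says.** Aim 3 in the Protocol Summary (Section I.c) is to "Determine the fetal/neonatal safety and adherence/tolerability of TMPS-AZ compared to TMPS". Its adverse birth outcomes in Section III.a include both "miscarriage (<28 weeks" and "stillbirth (>28 weeks", together with congenital anomaly and death within 7 days of birth.

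Section IX.a (Serious Adverse Event) lists six outcomes that make an event serious. Two concern the mother: her death, and "Unanticipated or prolonged maternal hospitalization (longer than expected". The other four concern the fetus or infant: stillbirth, a congenital anomaly, "Neonatal death", and, as the only item on infant admission, "Prolonged neonatal hospitalization (longer than expected based on gestational age at birth".

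There is no open-ended item. The investigator's view decides whether an event led to one of these outcomes. The text does not let that view extend the list.

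Section IX.b has the PI review safety data weekly and "report any serious adverse events to the DSMB and IRB and to NIH/NICHD". Section XIV.a promises both IRBs information on serious adverse events. Other adverse events reach the DSMB and NIH through quarterly reports (Section IX.b).

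Section VII.h has staff contact the mother every three months until the infant is one year old and ask for "any information about infant hospitalizations or sick clinic visits or death". The visit table in Section VII marks the adverse event form (Form 10) at those contacts. The Protocol Changes table shows that version 1.1 added this follow-up. The changes it lists do not include the SAE criteria.

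**The concern.** The SAE list and the data the trial collects do not match at two points.

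First, pregnancy loss is serious on one side of 28 weeks and not on the other, although the safety aim counts both. Eligibility requires a gestation below 28 weeks (Section V.b) and the first study dose is given at enrollment (Section VII.a). Every participant therefore starts treatment inside the miscarriage window.

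Second, infant deaths are asked about for a year, but only a neonatal death is serious, and the protocol does not say when the neonatal period ends.

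Section II says more data on this combination are needed in pregnancy. Fetal and infant deaths are among the events that the DSMB and IRBs would most want to see one by one. The DSMB's planned reviews of accumulating data are at 50% enrollment and at closeout, so between them it depends on the reporting streams.

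**Working it through.** No arithmetic applies. The check sets the event types beside the six criteria and then follows the reporting route for each.

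**Step 1: is the event on the list?**

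| Event | Where the plan collects it | Covered by one of the six SAE criteria? |
|---|---|---|
| Stillbirth (after 28 weeks) | Aim 3, Section III.a | Yes, by name |
| Miscarriage (before 28 weeks) | Aim 3, Section III.a | Not by name; only through the maternal hospitalization item, if the admission is unanticipated or prolonged |
| Death within 7 days of birth | Aim 3, Section III.a | Yes, as neonatal death |
| Infant death after the neonatal period | Section VII.h, to 12 months | No |
| Infant hospitalization after the neonatal period | Section VII.h, to 12 months | No |

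Of the three unlisted event types (miscarriage, later infant death, later infant hospitalization), 0 of 3 appear by name among the 6 criteria. The stillbirth item cannot take in miscarriage, because Section III.a separates the two at 28 weeks. As written, a loss at exactly 28 weeks falls under neither definition.

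**Step 2: what does each route provide?**

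| | Serious adverse event | Other adverse event |
|---|---|---|
| Relatedness | Study physician, including other possible causes (IX.a) | Graded by the clinician (IX.a) |
| PI | Weekly safety review (IX.b) | Weekly review, blinded to arm (XII) |
| DSMB and NIH | Each event reported; DSMB also evaluates it (IX.a, IX.b) | Quarterly reports; adverse events also in the interim report (IX.b) |
| IRBs | Reported and reviewed (IX.a, IX.b, XIV.a) | No route stated |

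**Step 3: is an infant event an adverse event at all?** Section IX.a words the definition around a subject who was given a pharmaceutical product. A miscarriage happens to the treated woman, so it qualifies. Under the plan an infant receives no study product, so the definition does not clearly reach an infant death, although Form 10 is scheduled at the infant contacts. For infants, therefore, even the right-hand column is not assured by the text.

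**Step 4: how long is the infant gap?** It runs from the end of the neonatal period to 12 months. Section IX.a sets no limit for neonatal. Section III.a gives 7 days, but only for early neonatal mortality. The start of the gap is thus undefined.

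**The case against.** The strongest reply is that these events are not lost. All adverse events are graded for relatedness, the PI sees them weekly, and the DSMB and NIH receive them quarterly. That stands, and it limits the point to event-level reporting, the fuller physician review and the IRB route.

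Several stronger readings are tempting, and the documents do not support them:

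- *The events escape expedited review, with a delay of a set length.* The protocol sets no expedited timeline and no SAE deadline, so there is no baseline from which to measure a delay.
- *Only SAEs are assessed for causality.* Section IX.a requires a relatedness judgment for every adverse event. The SAE route adds a study physician and consideration of other causes.
- *Every loss before 28 weeks is missed.* A miscarriage with an unanticipated or prolonged maternal admission already qualifies.
- *The gap is a stated share of the 12 months.* That needs a neonatal cut-off, which the plan does not give.
- *Later infant deaths and admissions are trial outcomes left off the list.* They are collected, but Section III does not list them as outcomes. Only miscarriage fits that description.
- *All infant admissions to 12 months should be serious.* The current list counts only prolonged neonatal stays, scheduled dosing is antenatal, and infant follow-up is optional at consent (Section XIV.b). Widening the list that far is a debatable trade-off.

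It is also fair that infant contacts are three months apart. SAE status would not shorten the time before a death is learned of. It would change only what happens afterwards.

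**Conclusion.** The omission is exact, and it matters in a narrow way. A miscarriage without a qualifying maternal admission, or an infant death after the neonatal period, is not serious under Section IX.a. It therefore misses study-physician review of other causes, event-level reporting to the DSMB, IRB and NIH/NICHD, and the only notice the IRBs are promised.

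The miscarriage half is the firmer one, since it is an inconsistency within the safety aim itself. The infant-death half is a mismatch between the SAE list and follow-up that version 1.1 added.

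The number of events affected cannot be given, because the documents state no expected rate of miscarriage or infant death and no share of miscarriages that would lead to a qualifying admission. The conclusion assumes that staff apply the list as written. It is a safety-reporting gap that should be closed. It does not affect the validity of the efficacy comparison.

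**What to change.** In Section IX.a:

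1. Add miscarriage (before 28 weeks) to the SAE list, and settle where a loss at exactly 28 weeks belongs.
2. Add any infant death through the last infant contact.
3. Define neonatal by a day limit.
4. State that infant events count as adverse events, and that SAE reporting runs to the last infant contact.
5. For infant hospitalizations after the neonatal period, state which are reported and by what route. They need not all be SAEs.

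The cost is about one protocol paragraph, review of the amendment by both IRBs (Section XIV.a requires this for any change), and what should be a small number of extra SAE reports in a trial of 308 women. The documents give no rates from which to put a figure on that number.
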